2. CLINICAL PERFORMANCE STUDY OBJECTIVES AND ENDPOINTS

2.1 PRIMARY STUDY OBJECTIVES

The study will be divided into a pilot and two stages:

- Pilot: The goal of the six-month pilot is to determine if the enrolment strategy (identifying eligible subjects via commercial recruitment platforms, NIHR Research Delivery Network Primary Care Networks and Specialist Diabetes Service Centres (SDSC)) is adequate, and to identify barriers and develop mitigation strategies to improve recruitment. Participants may also self-refer to the study following viewing study information found on the study website or displayed in Primary Care locations. The pilot will also assess the BMI distribution to determine whether body mass index (BMI) should be included as eligibility criteria in study stage 1 and 2. We will aim to open up to 450 Participant Identification Centres (PICs) during the pilot and at least 30 recruitment hubs where participants can attend for study visits (also referred to as sites).
- The pilot will be considered successful if:
 - Recruitment rate is greater than 10% of invitation to enrolment, or
 - 800 participants are enrolled, or
 - Enrolment is greater than an average of 133 participants per month in the last three months of pilot
- The feasibility of continuation to study stage 1 and 2 will be assessed by the Trial Steering Committee based on recruitment during the pilot
- Study stage 1 will enrol an additional 5,600 NOD participants with the primary objective to evaluate sensitivity and specificity of the Avantect test in detecting pancreatic cancer in 3,200 intervention arm participants with 1 year of follow-up for futility and efficacy.
- Study stage 2 will enrol an additional 8,600 participants to make a total of 15,000 NOD participants with the primary objectives of evaluating sensitivity and specificity of the Avantect test in detecting pancreatic cancer in intervention arm participants, and comparing the proportion of pancreatic cancers deemed resectable across the intervention and control arms.

2.2 PRIMARY ENDPOINTS:

- Pilot: Recruitment rate - number of NOD individuals enrolled into the study divided by the number of individuals invited to participate.
 - Recruitment rate to be greater than 10% of invitation to enrolment OR
 - 800 participants are enrolled OR
 - Enrolment is greater than an average of 133 patients per month in the last 3 months of the pilot.
- Study stage 1 and 2:

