7.6.4 Timepoint T3 (2 years after T2)

T3 refers to the three years of follow-up (following recruitment at T0) which will be collected via linkage with the cancer and mortality registry. At the time of writing the cancer registry is managed by the National Cancer Registration and Analysis Service which sits within NHS England, and the mortality register is managed by the Office for National Statistics but can be accessed through NHS England. Cancer and mortality registry data will still be required and sought even if the owner of the dataset changes in the future. A cancer and mortality registry download will be obtained on three

occasions: once 6,400 participants have been recruited, once 15,000 participants have been recruited, and at 3 years post last participant recruited.

Data Collection from Cancer Registry:

- Any cancer diagnosis (ICD10 C00-D48)
- Date of cancer diagnosis
- Site of cancer diagnosis
- Stage of cancer at diagnosis
- Histology of cancer
- Survival status
- Cancer treatments

Data Collection from Mortality Registry:

[figure not shown]
- Date of death
- Causes of death

The local site study team will collect and keep NHS number, address and contact details (including 1 or 2 phone numbers and an email address) from all participants. NHS numbers and dates of birth for all participants will be shared securely by site to the SCTU. SCTU will then pass on the NHS numbers and dates of birth to the administrators at the registries to allow them to perform registry searches on three occasions during the study. The local site team will also share with the SCTU study team, via secure email, the contact details (name, postal and email address) for a select number of participants (numbers to be defined) who have consented to optional further research questionnaire.

Addresses will be used by sites to contact participants with any Avantect “Detected” results by post. Phone numbers will be used by sites to contact participants if required throughout the study, including contacting participants to inform them of a “Detected” Avantect test if deemed more appropriate than by post alone (at the discretion of the clinical team).

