9.2 SAMPLE SIZE

Upon conclusion of the pilot, further recruitment to the study will occur with a planned interim analysis for futility and efficacy. Participants in the pilot study will continue to have their data analysed. The planned interim analysis is referred to as ‘stage 1’ analysis for convenience. The final analysis is referred to as ‘stage 2’ analysis. In each stage, there are three co-primary endpoints:

1. sensitivity (of the Avantect test),
2. specificity (of the Avantect test) and

3. resectability of diagnosed PCs

In the stage 1 interim analysis, these endpoints will be assessed within the intervention arm, as more information will be available on the diagnostic status of this group. In the stage 2 final analysis, the sensitivity and specificity of the test will be estimated within the intervention arm, whereas resectability will be compared between the arms.

The anticipated prevalence of a pancreatic cancer diagnosis within 3-years of follow-up within this population is 1%³. Conservative estimates place the anticipated sensitivity of the Avantect test at 65% sensitivity and 95% specificity in the detection of PC. Under usual care in the UK, 10-20%^{13,14} of pancreatic cancer patients receive surgery with curative intent due to the majority (80%) presenting at Stage III or Stage IV¹⁵. Data from the CAPS cohort¹⁶ in the US has demonstrated that it is possible to reduce the proportion of patients presenting with late stage disease if surveillance testing is conducted on at-risk subgroups, thus improving the availability of curative resection as a treatment strategy. It is hoped that the Avantect test can improve the resectability of pancreatic cancers from a rate of 14% in usual care to 40% in the intervention arm (just over a 2.5-fold increase).

With three co-primary endpoints, each endpoint must be reached for an overall successful result. To achieve an overall power of 90%, the power for each endpoint should be $90\%^{(1/3)} = 96.5\%$. Following guidance from Korevaar and colleagues¹⁷, the analysis will consist of a one-sided test at an cumulative alpha of 0.05 at the final analysis. Because there is an interim analysis at stage 1 for efficacy and futility, the one-sided significance level changes at the interim and final analysis.

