An analysis for futility and efficacy will be conducted once 3,200 individuals randomised to the intervention arm have returned for the third blood-draw (T2) in order to obtain cancer outcome data from the cancer registry. This amounts to 43.8 % of the total information accrual in the intervention arm, accounting for 2.5% not qualifying for the Per Protocol population (see 9.4; $3,200/7,312$). All individuals with one or more Avantect “detected” test results will be included as positive predictions. Individuals whose Avantect test results are all “not detected” will be included as negative predictions. Based on a cumulative one-sided alpha of 0.05 and 96.5% power for the three co-primary outcomes, the futility and efficacy thresholds at stage 1 interim analysis are detailed in the table below. If all study endpoints are deemed futile, or in the scenario that all study endpoints are deemed efficacious the study will stop at this stage. If all of the study endpoints are deemed promising then the study will continue to stage 2. If there is a combination of results, the Trial Steering Committee (TSC) and IDMC will decide whether the study progresses to stage 2.

	Expected proportion	Futility threshold at stage 1	Promising result range at stage 1	Efficacy threshold at stage 1
Sensitivity	65%	<46.5%	46.5% to 63.1%	>63.1%
Specificity	95%	<92.0%	92.0% to 94.9%	>94.9%
Resectability	40%	<21.0%	21.0% to 38.1%	>38.1%

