9.3 STUDY TIMEPOINTS

There will be three timepoints for blood collection: at baseline (T0), 6 months +/- 2 weeks post-baseline (T1), and 12 months +/- 2 weeks from baseline (T2). For each study timepoint, the Avantect test will be conducted. For samples collected from participants assigned to the intervention arm, the Avantect test will be assessed as soon as possible within 14 business days of receipt of samples in the analysing laboratory at ClearNote Health. Those with positive test results (test result = Avantect “detected”) in the intervention arm will undergo diagnostic pancreas imaging. Samples collected from participants assigned to the Control arm will be stored for potential future Avantect testing or future research.

The study design comprises a pilot and two study stages:

- Stage 1 Analysis will be carried out 6 months after the T1 visit for 3,200 participants in the intervention arm. Only participants followed up for a minimum of 6 months after the T1 visit in the intervention arm will be included in this analysis.
- Stage 2 Analysis will be carried out after 3-year follow-up data has been collected for all 15,000 participants.

In addition, during the study annual readouts will be provided to the data monitoring committee to monitor study progress and inform on decisions to continue or stop the study.

The diagnostic performance of the Avantect test results will be summarised according to the pancreatic cancer diagnoses collected by the point of analysis. The stage shift, and resection rate of pancreatic cancer will be summarised by arm. For this purpose, a positive test at any timepoint will be considered a ‘positive prediction’ e.g., if a participant has a negative result at T0, but a positive result at T1, their overall prediction will be considered as at-risk of pancreatic cancer.

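### For sensitivity and resectability, the 43.8% Stage 1 information fraction counts participants rather than diagnosed cancers, and Stage 1 sensitivity is biased upward because test-negative cancers surface later

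*Protocol*

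**What the plan says.** Section 9.2 places the interim analysis at the point where 3,200 intervention-arm participants have attended T2. It states that "This amounts to 43.8 % of the total information accrual in the intervention arm, accounting for 2.5% not qualifying for the Per Protocol population" (3,200/7,312). This one fraction serves all three co-primaries. The threshold tables in 9.2 and 9.4 call sensitivity futile below 46.5% and efficacious above 63.1%.

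The case numbers have a different time base. Section 9.2 says "The anticipated prevalence of a pancreatic cancer diagnosis within 3-years of follow-up within this population is 1" (per cent), and the 73 cancers per arm follow from that rate. Section 2.1 describes Stage 1 as covering "3,200 intervention arm participants with 1 year of follow-up for futility and efficacy", and section 9.3 adds: "Only participants followed up for a minimum of 6 months after the T1 visit in the intervention arm will be included in this analysis". The final analysis has a longer window: "Stage 2 Analysis will be carried out after 3-year follow-up data has been collected for all 15,000 participants".

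Under 7.8.1 and 9.3, intervention-arm participants with a detected result go to urgent referral and pancreatic imaging. Under 7.8.2, those with a not-detected result are neither told nor imaged. Section 7.6.4 schedules registry downloads "once 6,400 participants have been recruited, once 15,000 participants have been recruited, and at 3 years post last participant recruited".

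**The concern.** The precision of sensitivity and resectability depends on how many cancers have been diagnosed, not on how many people have been enrolled. A participant fraction equals a cancer fraction only if cases are as fully ascertained at Stage 1 as at the final analysis, and the protocol gives the two analyses different windows without adjusting for it.

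The missing cases are also not a random subset. A test-positive cancer enters the count soon after the test. A test-negative cancer enters only when it presents in routine care and reaches the study. An early cut therefore loses mainly false negatives, and observed sensitivity rises. At stake are the interim alpha, the meaning of the 46.5% and 63.1% thresholds, and the label that the oversight committees would see.

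**Working it through.** **The plan's own figure.** 3,200/7,312 = 43.8%. In cancers, 1% of 3,200 = 32 and 32/73 = 43.8%, but only with the full three-year yield. For specificity the fraction is right: 3,168/7,239 non-cases = 43.8%.

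**The fraction drives the design.** The protocol names no spending function, but the Pocock-type form α·ln(1 + (e − 1)t) at t = 0.438 gives 0.0140 for α = 0.025, which matches the 98.6% one-sided interval in 9.4. With the cumulative α of 0.05 in 9.2 it gives 0.028.

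**Assumptions.** There are 32 eventual cancers among the 3,200. Test-positive cancers are all known at Stage 1. A share f of test-negative cancers is known; f is not in the documents, so a range is shown. With true sensitivity s:
- cancers known = 32 × (s + (1 − s)f)
- information = cancers known/73
- apparent sensitivity = s/(s + (1 − s)f)
- P(observed > 63.1%) is exact, with TP ~ Bin(32, s) and FN known ~ Bin(32 − TP, f).

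Two nulls are used because section 9.2 gives 42% and section 9.4 gives 49%. Each cell shows 42% / 49%.

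| f | Cancers known | Information | Apparent sensitivity | P(> 63.1%) |
|---|---|---|---|---|
| 1 | 32.0 / 32.0 | 43.8% / 43.8% | 42.0% / 49.0% | 0.6% / 4.4% |
| 0.9 | 30.1 / 30.4 | 41.3% / 41.6% | 44.6% / 51.6% | 2.2% / 10.7% |
| 0.8 | 28.3 / 28.7 | 38.8% / 39.4% | 47.5% / 54.6% | 4.9% / 18.2% |
| 0.5 | 22.7 / 23.8 | 31.1% / 32.7% | 59.2% / 65.8% | 36% / 61% |

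Example, f = 0.8 and s = 0.42: 32 × (0.42 + 0.58 × 0.8) = 28.3 cancers; 28.3/73 = 38.8%; 0.42/0.884 = 47.5%.

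**Futility.** By the same method, a test with true sensitivity 42% falls below 46.5% with probability 65% at f = 1, 47% at f = 0.8 and 12% at f = 0.5.

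**Which f is plausible.** Section 4 says that most pancreatic cancers in this population are diagnosed within 12 to 18 months of the diabetes diagnosis. T0 is within about six months of that diagnosis, so T2 falls about 12 to 18 months after it. This makes 0.8 to 0.9 plausible, although section 4 gives no percentage and does not single out test-negative cancers.

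**Registry timing.** Assume linear accrual: 800 in 6 months, then 14,200/30 = 473 per month.
- 6,400 recruited (3,200 per arm): 6 + 5,600/473.3 = month 17.8.
- The last of these reaches T2 at month 29.8.
- Mean follow-up at month 17.8: (800 × 14.83 + 5,600 × 5.92)/6,400 = 7.0 months. Those with 12 months or more: 800 × 5.83/6 = 777, and 777/6,400 = 12%.
- Mean follow-up at month 29.8: 7.0 + 12 = 19.0 months.

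The download in 7.6.4 thus falls about 12 months before the trigger in 9.2, although 9.2 ties the wait for T2 to obtaining registry outcomes. If 7.6.4 governs, values of f well below 0.8 become plausible.

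**The case against.** Several points on the other side stand.

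- **Twelve months is a floor.** Section 9.3 sets a minimum, and at the assumed pace mean follow-up at the T2 trigger is about 19 months. With section 4, this favours the upper part of the f range, where information is only two to five percentage points below 43.8%.
- **Part of the excess at 49% has another cause.** With complete ascertainment the probability is already 4.4%, because a 63.1% threshold on about 32 cancers does not protect a 49% null. That comes from the separate conflict between 42% in 9.2 and 49% in 9.4.
- **Unfinished work-up pushes the other way.** If only 90% of test-positive cancers are confirmed at Stage 1, then at f = 0.8 the probabilities fall from 4.9% to 2.8% (null 42%) and from 18% to 12% (null 49%).
- **An efficacy stop needs all three co-primaries.** Mixed results go to the TSC and IDMC. At f = 0.8, with true resectability 40% and specificity 95% and assuming independence, the joint probability is about 1.7% (null 42%) or 6% (null 49%). Independence is doubtful, since resectability at Stage 1 uses the same cancers.

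A reader might infer that information is really about 15%: one third of 32 is 10.7, and 10.7/73 = 14.6%. That requires test-positive cancers to wait as long as test-negative ones, which the imaging pathway contradicts. A reader might also object that 3,200 is not reduced by 2.5% while 7,312 is. Like for like this gives 3,200/7,500 = 42.7%, which moves the interim alpha only from 0.0140 to 0.0138, and people who attend T2 are less likely to have no result at all.

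**Conclusion.** The point holds for sensitivity and resectability; 43.8% is correct for specificity. For those two endpoints it is an upper limit, reached only if no three-year cancer remains undiagnosed at Stage 1. At f = 0.8 to 0.9, with prompt diagnosis of test-positives and 32 eventual cancers, information is about 39–42%. The chance that a null test is labelled efficacious on sensitivity rises to 2–5% (null 42%) or 11–18% (null 49%), from 0.6% and 4% with complete ascertainment, against an intended 1.4% or 2.8%. Futility weakens from 65% to 47% at f = 0.8 for a true 42% test. Results are much worse at f = 0.5, which matters mainly if the registry schedule in 7.6.4 prevails over the trigger in 9.2.

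A reader might infer that a null test would probably be called efficacious, or that the trial could stop on sensitivity alone. The documents support neither. On average, a null test exceeds 63.1% only if f is below about 42% (null 42%) or 56% (null 49%), and section 4 points to higher values. The stopping rule requires all three endpoints. The harm is a biased label and a raised error rate for sensitivity.

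**What to change.** 1. In 9.2, define Stage 1 information for sensitivity and resectability as confirmed intervention-arm cancers divided by 73, and recompute the Stage 1 and final bounds from the observed count. Keep the participant fraction for specificity only.
2. Define Stage 1 sensitivity over a fixed ascertainment window, state that it overestimates 36-month sensitivity, and add a sensitivity analysis over f.
3. Reconcile 7.6.4 with 9.2 by taking the first registry download when the 3,200th intervention-arm participant reaches T2.

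The cost is protocol wording and a later registry request. The interim fraction and alpha become slightly smaller: at 39–42% information, the spending form above gives about 0.013 rather than 0.0140. Restricting Stage 1 sensitivity to futility would also address the bias, but it is not required, since the changes above keep the interim efficacy look.

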9.3 STUDY TIMEPOINTS

There will be three timepoints for blood collection: at baseline (T0), 6 months +/- 2 weeks post-baseline (T1), and 12 months +/- 2 weeks from baseline (T2). For each study timepoint, the Avantect test will be conducted. For samples collected from participants assigned to the intervention arm, the Avantect test will be assessed as soon as possible within 14 business days of receipt of samples in the analysing laboratory at ClearNote Health. Those with positive test results (test result = Avantect “detected”) in the intervention arm will undergo diagnostic pancreas imaging. Samples collected from participants assigned to the Control arm will be stored for potential future Avantect testing or future research.

The study design comprises a pilot and two study stages:

- Stage 1 Analysis will be carried out 6 months after the T1 visit for 3,200 participants in the intervention arm. Only participants followed up for a minimum of 6 months after the T1 visit in the intervention arm will be included in this analysis.
- Stage 2 Analysis will be carried out after 3-year follow-up data has been collected for all 15,000 participants.

In addition, during the study annual readouts will be provided to the data monitoring committee to monitor study progress and inform on decisions to continue or stop the study.

The diagnostic performance of the Avantect test results will be summarised according to the pancreatic cancer diagnoses collected by the point of analysis. The stage shift, and resection rate of pancreatic cancer will be summarised by arm. For this purpose, a positive test at any timepoint will be considered a ‘positive prediction’ e.g., if a participant has a negative result at T0, but a positive result at T1, their overall prediction will be considered as at-risk of pancreatic cancer.

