Clinical Performance Study Design:	Prospective, single blinded interventional randomised multicentre study
Sample size:	Up to 15,000 participants across the UK in the following stages: 
 • Pilot: target 800 participants • Study stage 1: up to an additional 5,600 participants • Study stage 2: up to an additional 8,600 participants There will be a data driven ‘stop-go’ decision at the end of each stage before progressing to the next stage.
Treatment/Intervention:	Participants will be blindly randomised into two arms; 
 • Intervention arm: Avantect test performed within prioritised time frame with intent to share only “detected” test results with the participants and their General Practitioners (GPs) in parallel to making a referral to the local secondary care clinical team for further investigations. All test results will be included in primary endpoint analysis. • Control arm (Standard of Care [SoC] arm): Participants will receive the current standard of care for diabetes management. Samples will be used for potential future Avantect testing and/or future research.
Number of specimens required per participant:	Three peripheral blood samples per participant (up to 30 mL in total) will be collected at three timepoints
Duration of the clinical performance study:	Participant involvement on trial: 3 visits over 12 months Length of remote follow-up collection for each participant: 36 months from consent Recruitment duration: 36 months Total study duration (including 12m analysis and report writing): 7 years

URL for Database:	https://www.imedidata.com
URL for randomisation:	https://www.imedidata.com

Primary Study Endpoints:	Pilot: Recruitment rate Study stage 1 & 2: Sensitivity and specificity of Avantect test for detecting pancreatic cancer, pancreatic cancer resectability rate
---------------------------------	--

Secondary Study Endpoints:	Secondary endpoints (pilot and study stage 1 and 2 combined) will include pancreatic cancer stage shift, PPV, NPV and proportion of pancreatic cancer patients undergoing surgical resection
Exploratory Endpoints	Overall survival (time-to-event) Time to pancreatic cancer diagnosis (NOD to pancreatic cancer diagnosis) 6-item Spielberger State Trait Anxiety Inventory (STAI) Performance characteristics for high-grade neoplasia
Total Number of Sites:	Up to 3,000 GP practices and up to 200 Specialist Diabetes Service Centres

TRIAL SCHEMA

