 - Sensitivity of Avantect test for detecting PC – number of individuals in the intervention arm with one or more Avantect “detected” test results and PC divided by the number of individuals in the intervention arm with PC.
 - Specificity of Avantect test for ruling out PC – number of individuals in the intervention arm with no Avantect “detected” test results, at least one Avantect “not detected” test result and no diagnosis of PC divided by the number of individuals in the intervention arm with no diagnosis of PC.
 - Resectability rate – number of individuals with PC deemed resectable by the study multidisciplinary team (MDT) divided by the number of PCs.

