4. OVERALL TRIAL DESIGN

A prospective, single blinded interventional randomised controlled multicentre study with a pilot followed by 2 stages of recruitment. Selected pre-existing conditions of interest, STAI, body measurements and blood samples will be collected at enrolment (Baseline (T0)), and at 6 months intervals (T1 and T2)). Three cancer and mortality registry searches will be undertaken by the SCTU study team to assess any cancer diagnosed and deaths during the Follow-up study period (T3) (Figure 1). Cancer registry database will be interrogated using any “C-codes and D-codes” available and data from any cancer type will be collected. Peer reviewed published data by the study team¹² has shown that the vast majority of pancreatic cancer patients are diagnosed, in NOD subjects, within 12 -18 months from type 2 diabetes diagnosis. Therefore, the study strategy is to test NOD patients at baseline (T0) (within 6 months from diabetes diagnosis) and thereafter at 6 and 12 months from T0 to ensure that the Avantect test is used in the period before pancreatic cancer symptoms usually present.

[figure not shown]

Figure 1: SAFE-D visit schedule figure

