9.4 STATISTICAL ANALYSIS PLAN (SAP)

This study will be analysed using the principles of the International Conference on Harmonisation E9 guidelines and reported according to the CONSORT guidelines. A full and detailed statistical analysis plan will be developed prior to the final analysis of the study. The main features of which are described here.

All analyses will be conducted on a Per Protocol population. All individuals in the control arm will qualify for the Per Protocol population. Individuals in the intervention arm will qualify for the Per Protocol population if they have at least one analysable Avantect test result (i.e. either “Detected” or “Not detected”). Per Protocol population will be analysed according to the original randomisation

group even when other aspects of the protocol are not followed e.g.unplanned cross-over, study withdrawal. It is expected that 98.8% of the randomised population will qualify for the Per Protocol population.

The co-primary outcomes are Avantect sensitivity and specificity in detecting PC, and resectability rate. Sensitivity is defined as the proportion of participants in the intervention arm with one (or more) Avantect “detected” test results who have pancreatic cancer diagnosed via imaging in relation to all individuals in the intervention arm who had pancreatic cancer diagnosed. Specificity is defined as the proportion of participants in the intervention arm with one or more Avantect “not detected” test results, and no Avantect “detected” results, who did not have a pancreatic cancer diagnosis in relation to all individuals in the intervention arm who did not have a pancreatic cancer diagnosis. Resectability is defined as the proportion of PCs deemed resectable by the study MDT divided by the number of PCs and will be compared between arms. For all co-primary endpoints, a logistic model will be used to estimate uncertainty. At the stage 1 interim analysis, due to alpha spending to reach a cumulative total alpha of 0.025 for each co-primary endpoint, a one-sided 98.6% confidence interval will be calculated to estimate the lower-bound of the observed proportion. At the stage 2 final analysis, a one-sided 98.5 % one-sided interval will be calculated instead. Co-primary endpoints will also be assessed for regular oversight meetings, where a one-sided 95% confidence interval will be used.

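### The final accuracy analysis has no stated diagnosis window: section 9.3 counts every pancreatic cancer collected by the analysis date, which conflicts with the 36 months per participant given elsewhere

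*Protocol*

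**What the plan says.** **Counting rule.** Section 9.3 states: "The diagnostic performance of the Avantect test results will be summarised according to the pancreatic cancer diagnoses collected by the point of analysis". Nothing else in the protocol says which diagnoses are counted.

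**Endpoint definitions.** In section 2.2 the sensitivity numerator is "divided by the number of individuals in the intervention arm with PC". Section 9.4 takes the test-positive cancers "in relation to all individuals in the intervention arm who had pancreatic cancer diagnosed". The table in section 2.4 is equally open. None sets a maximum time from T0 or from the last test.

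**Testing.** Blood is drawn at T0, 6 months and 12 months, so testing ends at month 12.

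**Registry data.** Section 7.6.4 plans three downloads. The first comes at 6,400 recruits; the other two come "once 15,000 participants have been recruited, and at 3 years post last participant recruited". The synopsis gives a recruitment period of 36 months.

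**Signs of a 36-month window.** The synopsis says "Length of remote follow-up collection for each participant: 36 months from consent". Section 7.6.4 describes T3 as three years from T0. Section 9.3 places the Stage 2 analysis after 3-year data exist for all 15,000 participants. Section 9.2 sets at 1% "The anticipated prevalence of a pancreatic cancer diagnosis within 3-years of follow-up within this population", and this rate yields the 73 cases per arm.

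**Timing of cancers.** Section 4 reports that "the vast majority of pancreatic cancer patients are diagnosed, in NOD subjects, within 12 -18 months from type 2 diabetes diagnosis".

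**The concern.** Sensitivity is a co-primary endpoint judged against a fixed null. If every cancer in the final download counts, its denominator depends on when each participant happened to be recruited. The last recruits contribute 36 months of diagnoses and the first contribute up to twice that, all with testing that stopped at month 12. A cancer diagnosed after month 36 in someone whose results were all negative becomes a false negative. Such cancers are outside the 73 cases on which the design rests. The same open rule feeds PPV, NPV and the denominators of resectability, stage shift and resection.

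The sections can be read two ways, and the choice changes which cancers enter a co-primary. If it is settled once outcomes are known, the window can be chosen with its effect on the result in view.

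**Working it through.** **1. The plan's own figures.**
- 73/0.975 gives 75 cases per arm; 75/0.01 = 7,500 per arm; 7,500 × 0.975 = 7,312; 7,312 × 1% = 73 cases.
- 73 × 65% = 47.5, shown as 48. Non-cases: 7,239 × 95% = 6,877.
- Section 9.2 claims 96.5% power to exclude 42% sensitivity. With n = 73 and true sensitivity 65%, exact binomial power is 97.3% at one-sided 0.03 and 95.4% at 0.015, so the claim is reproduced to within about a point.
- These 73 cases are cancers within 3 years, by the wording of section 9.2.

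**2. Calendar under the literal rule.**
- First recruit to final download: 36 + 36 = 72 months, which is 60 months after the last test.
- Last recruit to final download: 36 months, which is 24 months after the last test.
- Assumed accrual: 800 in months 0 to 6 (the pilot) and 14,200 evenly over months 6 to 36. Mean follow-up beyond month 36 = (800 × 33 + 14,200 × 15)/15,000 = 15.96 months.

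**3. Extra late cases (assumption).** The documents give no incidence after month 36. Extra cases = 7,312 × (15.96/12) × annual rate. Rates of 0.05%, 0.10% and 0.15% a year give 4.9, 9.7 and 14.6, rounded to 5, 10 and 15. The plan's average over the first 3 years is 1%/3 = 0.33% a year, so these are roughly 15%, 30% and 45% of it.

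**4. Effect on sensitivity.** Assume late cancers are flagged only at the test's 5% false-positive rate. Expected sensitivity = (48 + 0.05 × extra)/(73 + extra). Power is exact binomial at one-sided 0.03. It is shown against both nulls because section 9.2 plans against 42% and the success rule in section 9.4 uses 49%.

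| Extra late cases | Sensitivity | Power vs 49% | Power vs 42% |
|---|---|---|---|
| 0 | 48/73 = 66% | 81% | 98% |
| 5 | 48.25/78 = 62% | 57% | 94% |
| 10 | 48.5/83 = 58% | 41% | 87% |
| 15 | 48.75/88 = 55% | 21% | 69% |

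**5. Specificity.** Moving 15 people from non-cases to cases leaves 7,224 non-cases. If 5% of those moved were flagged, the rate among the rest stays at 95%.

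**6. With a 36-month cap.** Cancers diagnosed up to 36 − 12 = 24 months after T2 still count as false negatives when all results were negative. If 10% of the 73 cases were late in this sense and flagged at 5%, sensitivity would be 0.90 × 65% + 0.10 × 5% = 59%.

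**The case against.** The strongest reply is that the window is already 36 months. The synopsis gives that length for each participant, section 7.6.4 defines T3 as three years from T0, section 9.2 ties the 1% to 3 years, and section 9.3 times Stage 2 by 3-year data. On this view the sentence in section 9.3 is generic, covering the interim, final and annual readouts alike, and the final download is only when data are extracted.

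Much of this stands. A reader might infer that the protocol sets follow-up of 36 to 72 months. It does not: that range appears only when the section 9.3 rule is joined to the download date and the 36-month statements are set aside. But those statements describe length of data collection, the basis of the event rate and timing of the analysis. None says which diagnoses count, and the one sentence that does has no limit.

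A reader might also infer that the tests could not have seen the late cancers. The documents do not show this; the 5% flag rate is an assumption. Section 4 suggests late cases are few, so the larger scenarios may overstate the loss. Much of the low power against 49% reflects the separate 42%/49% conflict: with no late cases it is already 81%, against 98% for the 42% null.

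Lastly, cumulative 36-month sensitivity is a legitimate estimand. That is why the shorter window is proposed only as supportive.

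**Conclusion.** The point holds as an internal conflict over the counting window for a co-primary endpoint. Section 9.3 and the endpoint definitions set no limit; the synopsis and sections 7.6.4 and 9.2 point to 36 months. Followed literally, the rule makes sensitivity depend on recruitment date and departs from the 3-year basis of the 73 cases.

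The size is illustrative. It rests on assumed accrual, assumed incidence after month 36 and the assumed 5% flag rate. On those assumptions even 5 extra cases cost about 4 points of sensitivity, with 24 points of power lost against the 49% null or 4 against the 42% null. The bias works against the test, so this is not a route to false success, and specificity is essentially unaffected. Dilution of the between-arm endpoints was not quantified.

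This should be corrected before outcome data are seen. It is more than a detail for the SAP, because the protocol already states a counting rule and that rule conflicts with its own follow-up period.

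**What to change.** - In sections 2.2, 9.3 and 9.4, define the cancers counted in the Stage 2 endpoints as those diagnosed within 36 months of T0, for every participant. This replaces the analysis-date rule for Stage 2 and agrees with the synopsis and sections 7.6.4 and 9.2. Stage 1 and the annual readouts can keep the current rule.
- Pre-specify a supportive estimate of sensitivity, specificity, PPV and NPV counting cancers diagnosed within 12 months of the participant's last analysable test. This shows how far the primary figure depends on cancers that surface well after testing ended.

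The cost is protocol and SAP wording. Section 7.6.4 already collects the date of cancer diagnosis, so no new data are needed. The small downside is that cancers diagnosed after month 36 in early recruits leave the primary analysis. They were never part of the planned 73 per arm and can be reported descriptively.
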